
Treatment period (open): All patients who consent to study participation will start treatment with INC424 upon meeting all study eligibility criteria. The study period commences on Day 1 (day of first dose of study drug) and continues until either:

- a. Disease progression;
- b. Transplant;
- c. Unacceptable toxicity;
- d. Death;
- e. Discontinuation from the study for any other reason;
- f. Physician decision
- g. Withdrawal of consent;
- h. Until 24-months after LPFV; or
- i. Until the drug becomes commercially available, whichever occurs first

[figure not shown]
Should INC424 not be available to patients after the drug is commercialized or 24-months after LPFV, Novartis will have a local transition plan in place to ensure that patients have access to INC424 without delays to treatment. Once the last dose of INC424 open label study drug is taken, or it becomes commercially available in each participating country or 24-months after LPFV, no further AEs/SAEs will be collected after the required Study Completion (see [Section 7.6.3](#)).

End of study / treatment: Day of last dose of open-label INC424.

Follow-up period: 28 days following the last dose of open-label INC424.

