A dose reduction occurs when a non-missing total daily dose record is followed by a record with a smaller total daily dose. A dose reduction may or may not have a dose interruption in between.

For details see protocol section 6.2.2. Some hypothetical examples are provided here:

If an investigator advises a patient to go from (say)

- 20 mg to a halt/stop and then go to 15 mg, that would be considered a dose interruption and also a dose reduction*
- 20 mg to 15 mg without a halt/stop in between – there is a dose reduction here, but no dose interruption*
- 20 mg to 15 mg after a halt/stop, but the patient never returns to the study, this will be considered a permanent study drug discontinuation*

In the case of a dose escalation, say, from 10 mg to 15 mg, there should not be any dose interruption in between.

Imputation rule for missing/partial dates of study drug

The following rule should be used for the imputation of the dose end date:

Scenario 1: If the dose end date is completely missing and there is no EOT page and no death date, the patient is considered as on-going:

The patient should be treated as on-going and the cut-off date should be used as the last dosing date.

Scenario 2: If the dose end date is completely or partially missing and the EOT page is available:

Case 1: The dose end date is completely missing, and the EOT completion date is complete (date of death is available in the EOT page), then this latter date should be used.

Case 2: Only Year(yyyy) of the dose end date is available and yyyy < the year of EOT date or only year of EOT date is available:

Use Dec31yyyy

Case 3: Only Year(yyyy) of the dose end date is available and yyyy = the year of EOT date:

Use EOT date

Case 4: Both Year(yyyy) and Month (mm) are available for dose end date, and yyyy = the year of EOT date and mm <= the month of EOT date:

Use last day of the Month (mm)

Case 5: Both dose end date and EOT date are completely missing:

Use the last contact data across all panels in the database.

After imputation, compare the imputed date with start date of treatment, if the imputed date is less than the start date of treatment:

Use the treatment start date

Patients with missing start dates are to be considered missing and no imputation will be made. If start date is missing then end-date should not be imputed.

3.3 Concomitant medication:

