3.4.1 Primary endpoints

3.4.1.1 Variables

The analysis of the primary endpoint will be performed on the incidence by patients of **treatment-emergent AEs** considering or not certain AEs characteristics (e.g. relationship to study medication, severity).

Incidence of a given AE is defined as the ratio of total number of patients experiencing the given AE at least once (defined by its preferred term [PT]) divided by the total number of patients at risk (i.e. part of the safety set).

A treatment-emergent AE is an AE that first occurs or worsens during treatment (including the 28 days following last treatment administration).

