3.4.1.2 Analysis

No hypotheses or models will be considered for these analyses, descriptive statistics will be provided.

In this section the term adverse event or AE refers only to treatment-emergent AEs unless specified otherwise.

The treatment-emergent AEs will be summarized, while all reported AEs will be included in listings.

The incidence of AEs will be tabulated using MedDRA (Medical Dictionary for Regulatory Activities) preferred term and system organ class (SOC).

Incidence of AEs will also be summarized by system organ class, severity (based on CTC AE grades version 3.0).

The same analysis will be repeated for SAEs regardless of drug relationship, drug related SAEs, AEs which CTCAE grade is 3 or 4 and for drug related AEs.

The following AEs will be summarized –

- AEs by primary system organ class (SOC), preferred term and maximum grade
- AEs suspected to be study drug related by primary system organ class, preferred term and maximum grade

- AEs leading to study drug discontinuation by primary system organ class, preferred term and maximum grade
- Serious adverse events will be analyzed, by primary system organ class, preferred term and maximum grade

Separate summaries for on-treatment and all on-study deaths (on-treatment and post-treatment) will be produced by system organ class and preferred term. All deaths collected in the database will be listed and post treatment and post-follow-up deaths will be flagged.

Note: The death summaries cover subjects from the Safety Set. The count of deaths in safety analyses could be different from the number of deaths in the efficacy analyses.

Data handling rules for death:

The following rule will be used for the analysis of deaths:

1. **On-treatment deaths:** If date of death is within 28 days following last treatment administration or study evaluation completion visit i.e.
date of death ≤ min (last dose date + 28 days; study evaluation completion visit date)
2. **Post-treatment deaths:** If date of death is greater than 28 days after treatment end date but before the study evaluation completion visit i.e.
(Last dose date + 28 days) < date of death ≤ study evaluation completion visit date
3. **Post-follow up deaths:** If date of death is after the end of study evaluation completion visit i.e. *date of death > study evaluation completion visit date*

3.4.2 Secondary endpoints:

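### SAP 3.2, Case 4: a partial dose end date in the EOT month is imputed to month end with no cap, so the last dose can fall up to 30 days after EOT or after death

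*SAP*

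**What the plan says.** The imputation rules in SAP 3.2 (missing or partial dates of study drug) distinguish several cases when an EOT page exists.

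- **Case 3** applies when "Only Year(yyyy) of the dose end date is available and yyyy = the year of EOT date". The EOT date is then used.
- **Case 4** applies when year and month are both known, with "yyyy = the year of EOT date and mm <= the month of EOT date". The instruction is "Use last day of the Month (mm", where mm is the known month.
- **Final check:** "After imputation, compare the imputed date with start date of treatment, if the imputed date is less than the start date of treatment", the treatment start date is substituted. There is no corresponding check against the EOT date or the date of death.

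Protocol 4.1 defines end of study / treatment as "Day of last dose of open-label INC424". The protocol glossary takes the later of the final evaluation visit and drug discontinuation. Under either definition the last dose cannot come after EOT.

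The last dose date is then used in three places:

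- **Exposure (SAP 3.2):** last administration date minus first non-zero dose date, plus one day. This is also the denominator of dose intensity.
- **Primary endpoint (SAP 3.4.1.1):** "A treatment-emergent AE is an AE that first occurs or worsens during treatment (including the 28 days following last treatment administration".
- **On-treatment deaths (SAP 3.4.1.2):** "date of death ≤ min (last dose date + 28 days; study evaluation completion visit date".

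**The concern.** Case 4 admits the EOT month, and month end is on or after any EOT date in that month. The rule therefore produces last-dose dates that the protocol's own definition excludes. If the patient died in that month, it can record dosing after death. Case 3 has less information but cannot pass EOT, because it uses the EOT date. The plan gives no reason for capping one case and not the other.

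What is at stake is the accuracy of exposure and dose intensity and, for the patients concerned, the boundary of the treatment-emergent window behind the primary endpoint and the split between on-treatment and post-treatment deaths.

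**Working it through.** The plan gives no figure to reproduce, and no sample size or power figure bears on the point. The check applies the rules as written.

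**Inputs**
- Case 4, Case 3, the final check, and the exposure and dose-intensity formulas: SAP 3.2.
- Treatment-emergent window, last administration + 28 days: SAP 3.4.1.1.
- On-treatment death window, the earlier of last dose + 28 days and the completion visit: SAP 3.4.1.2.
- Follow-up visit 28 to 37 days after last dose: Protocol 7.6.1.

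**Step 1. Overshoot past EOT.** Let k = (last day of month mm) − (EOT date).
- If mm is the EOT month, has n days, and EOT is on day d, then k = n − d. The smallest value is 0 (EOT on the last day). The largest is 31 − 1 = 30 (EOT on day 1 of a 31-day month).
- If mm is earlier than the EOT month, k is at most −1, so the rule never overshoots.
- Taking every calendar date in 2012–2016 as a possible EOT date gives 1,827 dates, of which 60 are month ends. Hence k > 0 for (1,827 − 60)/1,827 = 1,767/1,827 = 96.7% of dates, with mean k 14.7 and median 15. These figures describe the calendar with all dates weighted equally. They say nothing about how many patients are affected.

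**Step 2. Exposure.** Duration increases by k, so by up to 30 days relative to EOT.

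**Step 3. Dose intensity** = cumulative dose / duration of exposure. The denominator rises by k. The SAP does not say whether cumulative dose is also summed to the imputed date, so the net direction is open. As an illustration, assume the numerator stays fixed and k = 30. With EOT on Day 84 the ratio is 84/114 = 0.74 of its capped value; on Day 336 it is 336/366 = 0.92. If dosing is carried forward at an unchanged dose, dose intensity does not move.

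**Step 4. Treatment-emergent window.** The end is EOT + k + 28, at most 30 + 28 = 58 days after EOT. Example: EOT on 1 March 2014 and a dose end date of March 2014 with the day missing. The imputed last dose is 31 March, and the window ends on 28 April. Capped at EOT, it would end on 29 March.

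**Step 5. On-treatment death window.** Suppose the completion visit is v days after EOT. The window ends at day min(k + 28, v) as written, and at min(28, v) with the cap. For k = 30:

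| Visit day v | As written | Capped | Extra days |
|---|---|---|---|
| 28 | 28 | 28 | 0 |
| 30 | 30 | 28 | 2 |
| 37 | 37 | 28 | 9 |

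An on-schedule visit limits the widening to 0–9 days. A late visit would allow more.

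**Step 6. With the cap.** The imputed date is min(last day of mm, EOT date), so the overshoot is never above 0. Results for months before the EOT month do not change.

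**The case against.** The case against any material consequence is substantial, and most of it stands.

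- **Safety cut-off.** SAP 3.5 ends safety reporting 28 days after the end-of-treatment date. SAP 3.2 treats EOT date and dose end date as separate variables. If SAP 3.5 means the EOT date, reporting stops at EOT + 28 whatever Case 4 imputes, and the 58-day window does not arise. The SAP does not say which is meant.
- **Deaths.** A reader might infer that deaths up to 30 days later become on-treatment. The completion-visit bound prevents that when the visit is on schedule. A death on the EOT date itself is on-treatment under either date, provided the completion visit does not precede it, and no event can start afterwards; only exposure and possibly dose intensity change. The SAP does not say how the minimum is taken when no completion visit took place.
- **Few events to reclassify.** Protocol 9.1.1 requires adverse event recording to 28 days after the last dose (elsewhere in that section, at least 28 days). Under Protocol 9.2.2, later serious events are reported only if a causal link is suspected.
- **Narrow trigger.** For patients who discontinued, SAP 3.2 takes the last dose date from the EOT page. Protocol 7.6 requires the stop date on the eCRF, and Protocol 10.4 has missing values queried.
- **What the 30 days measure.** They might be read as error against the true stop date. Any month-end rule has that maximum error: a true stop on 1 January with EOT in March is imputed to 31 January, and the cap does not alter this. The defect is overshoot past EOT.
- **Comparison with Case 3.** It does not follow that knowing the month is generally worse than knowing only the year. For months before the EOT month, Case 4 comes closer to the true stop than Case 3 does. The inconsistency is confined to the EOT month.

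These points limit the consequences. They do not make a last dose after EOT or after death possible under the protocol.

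**Conclusion.** Case 4 is wrong as written, with a small expected impact. When the known month is the EOT month and EOT is not its last day, the imputed last dose falls 1 to 30 days after EOT. The overstatement of exposure, by up to 30 days relative to EOT, follows directly. The 58-day treatment-emergent window is a conditional maximum: it requires EOT on day 1 of a 31-day month and a safety cut-off that follows the imputed date. The 0–9 days for deaths assumes an on-schedule completion visit.

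A reader might go further and infer that primary adverse event incidence is materially inflated. The documents do not support this: they give no count of partial dose end dates, and collection beyond 28 days is limited. The study is also single-arm and descriptive, so no hypothesis test depends on the result.

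**What to change.** In Case 4, use min(last day of month mm, EOT date, date of death), ignoring any component that does not apply. Extend the final check so that no imputed dose end date exceeds the EOT date or the date of death, alongside the existing floor at treatment start. State in SAP 3.5 whether the end-of-treatment date means the EOT date or the (possibly imputed) last dose date, since this decides whether the 58-day window can occur. The cost is one line in SAP 3.2, a clarifying phrase in SAP 3.5 and a minor programming change. No new data are needed.

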3.4 Primary and secondary endpoints analyses

This section describes the planned statistical analyses for Section 11 of the clinical study report. Full analysis set will be used for efficacy data.

3.4.1 Primary endpoints

3.4.1.1 Variables

The analysis of the primary endpoint will be performed on the incidence by patients of **treatment-emergent AEs** considering or not certain AEs characteristics (e.g. relationship to study medication, severity).

Incidence of a given AE is defined as the ratio of total number of patients experiencing the given AE at least once (defined by its preferred term [PT]) divided by the total number of patients at risk (i.e. part of the safety set).

A treatment-emergent AE is an AE that first occurs or worsens during treatment (including the 28 days following last treatment administration).

3.4.1.2 Analysis

No hypotheses or models will be considered for these analyses, descriptive statistics will be provided.

In this section the term adverse event or AE refers only to treatment-emergent AEs unless specified otherwise.

The treatment-emergent AEs will be summarized, while all reported AEs will be included in listings.

The incidence of AEs will be tabulated using MedDRA (Medical Dictionary for Regulatory Activities) preferred term and system organ class (SOC).

Incidence of AEs will also be summarized by system organ class, severity (based on CTC AE grades version 3.0).

The same analysis will be repeated for SAEs regardless of drug relationship, drug related SAEs, AEs which CTCAE grade is 3 or 4 and for drug related AEs.

The following AEs will be summarized –

- AEs by primary system organ class (SOC), preferred term and maximum grade
- AEs suspected to be study drug related by primary system organ class, preferred term and maximum grade

- AEs leading to study drug discontinuation by primary system organ class, preferred term and maximum grade
- Serious adverse events will be analyzed, by primary system organ class, preferred term and maximum grade

Separate summaries for on-treatment and all on-study deaths (on-treatment and post-treatment) will be produced by system organ class and preferred term. All deaths collected in the database will be listed and post treatment and post-follow-up deaths will be flagged.

Note: The death summaries cover subjects from the Safety Set. The count of deaths in safety analyses could be different from the number of deaths in the efficacy analyses.

Data handling rules for death:

The following rule will be used for the analysis of deaths:

1. **On-treatment deaths:** If date of death is within 28 days following last treatment administration or study evaluation completion visit i.e.
date of death ≤ min (last dose date + 28 days; study evaluation completion visit date)
2. **Post-treatment deaths:** If date of death is greater than 28 days after treatment end date but before the study evaluation completion visit i.e.
(Last dose date + 28 days) < date of death ≤ study evaluation completion visit date
3. **Post-follow up deaths:** If date of death is after the end of study evaluation completion visit i.e. *date of death > study evaluation completion visit date*

3.4.2 Secondary endpoints:

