9.1 Adverse events

9.1.1 Definition and reporting

[figure not shown]
An adverse event is defined as the appearance of (or worsening of any pre-existing) undesirable sign(s), symptom(s), or medical condition(s) that occur after patient's signed informed consent has been obtained. Abnormal laboratory values or test results occurring after informed consent constitute adverse events only if they induce clinical signs or symptoms, are considered clinically significant, require therapy (e.g., hematologic abnormality that requires transfusion or hematological stem cell support), or require changes in study medication(s).

Adverse events that begin or worsen after informed consent should be recorded in the Adverse Events eCRF. Conditions that were already present at the time of informed consent should be recorded in the Medical History eCRF. Adverse event monitoring should be continued for at least 28 days following the last dose of study treatment. Adverse events (including lab abnormalities that constitute AEs) should be described using a diagnosis whenever possible, rather than individual underlying signs and symptoms. When a clear diagnosis cannot be identified, each sign or symptom should be reported as a separate Adverse Event.

Adverse events will be assessed according to the CTCAE version 3.0. If CTCAE grading does not exist for an adverse event, the severity of mild, moderate, severe, and life-threatening, corresponding to Grades 1 - 4, will be used. CTCAE Grade 5 (death) will not be used in this study; rather, information about deaths will be collected through a Death form.

The occurrence of adverse events should be sought by non-directive questioning of the patient (subject) during the screening process after signing informed consent and at each visit during the study. Adverse events also may be detected when they are volunteered by the patient (subject) during the screening process or between visits, or through physical examination, laboratory test, or other assessments. As far as possible, each adverse event should be evaluated to determine:

- The severity grade (CTCAE Grade 1-4)
- Its duration (Start and end dates)
- Its relationship to the study treatment (Reasonable possibility that AE is related: No, Yes) or its relationship to the study treatment (Reasonable possibility that AE is related: No, Yes, investigational treatment, Yes, the study treatment (non-investigational), Yes, both and/or indistinguishable)

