9.2 Serious adverse events

9.2.1 Definitions

A serious adverse event (SAE) is defined as one of the following:

[figure not shown]
- Is fatal or life-threatening
- Results in persistent or significant disability/incapacity
- Constitutes a congenital anomaly/birth defect
- Is medically significant, i.e., defined as an event that jeopardizes the patient or may require medical or surgical intervention to prevent one of the outcomes listed above
- Requires inpatient hospitalization or prolongation of existing hospitalization, unless hospitalization is for:
 - Routine treatment or monitoring of the studied indication, not associated with any deterioration in condition
 - Elective or pre-planned treatment for a pre-existing condition that is unrelated to the indication under study and has not worsened since signing the informed consent
 - Treatment on an emergency outpatient basis for an event not fulfilling any of the definitions of a SAE given above and not resulting in hospital admission
 - Social reasons and respite care in the absence of any deterioration in the patient's general condition

Progression of myelofibrosis, including leukemic transformation (including fatal outcomes) are exempted from SAE reporting.

This information is collected in the study as part of study endpoints: progression free survival (PFS) and acute myeloid leukemia free survival (LFS).

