2.1 Analysis sets

Full Analysis Set (FAS) consists of all patients who received at least one administration of study drug.

Safety Set (SS) consists of all patients who received at least one dose of study drug and had at least one post-baseline safety assessment.

Please note: the statement that a patient had no adverse events (on the Adverse Event CRF) constitutes a safety assessment. Patients who have received at least one dose of study drug but who have no post-treatment safety data of any kind would be excluded from the safety population.

Per protocol set (PPS) consists of all FAS patients without any major protocol deviation.

The following major protocol deviations will lead to exclusion from the PPS:

- Male or female patients aged < 18 years of age at screening (Deviation code: I03)
- Unconfirmed diagnosis of PMF, PPV-MF or PETMF at screening (Deviation code: I04).
- Secondary MF (PPV-MF or PETMF) grade 0 and 1 for Fibrosis on scale 0-3. or grade 0, 1 and 2 on scale 0-4 at screening (Deviation code: I13).

The Full analysis set will be used for all population and efficacy analyses, while Safety set will be used for treatment administration description and safety analyses.

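### The death summary tables and the adverse-event denominator rest on a Safety Set that can leave out a treated patient whose only post-dose record is a Death form

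*SAP*

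**What the plan says.** SAP 2.1 and protocol 11.2 define the Full Analysis Set (FAS) as every patient given study drug at least once. The narrower set is defined so: "Safety Set (SS) consists of all patients who received at least one dose of study drug and had at least one post-baseline safety assessment". The same sections add that "the statement that a patient had no adverse events (on the Adverse Event CRF) constitutes a safety assessment", and that dosed patients "who have no post-treatment safety data of any kind would be excluded from the safety population".

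SAP 2.1 assigns the FAS to efficacy, which includes OS, and the Safety Set to safety. The Safety Set is also the denominator of the primary variable, the incidence of treatment-emergent adverse events (protocol 11.5.1, SAP 3.4.1.1). For deaths, SAP 3.4.1.2 says "Note: The death summaries cover subjects from the Safety Set" and continues "The count of deaths in safety analyses could be different from the number of deaths in the efficacy analyses". It gives no reason and plans no reconciliation. The same section lists every death held in the database, without limiting the listing to the Safety Set.

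On data capture, protocol 9.1.1 does not use CTCAE Grade 5; instead "information about deaths will be collected through a Death form". Protocol 9.2.1 states: "Progression of myelofibrosis, including leukemic transformation (including fatal outcomes) are exempted from SAE reporting".

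**The concern.** Membership of the Safety Set depends on something that happens after treatment starts, and death is one of the events that can prevent it. The first scheduled visit after Day 1 is Week 4 (protocol 7.5). Fatal progression and leukemic transformation need no SAE report, and worsening of disease symptoms is normally not an adverse event (protocol 9.1.1.1). An early progression death could thus leave a Death form and nothing else. SAP 2.1 settles that a nil adverse-event entry qualifies a patient; it does not settle whether a Death form does.

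Such a patient would leave both numerator and denominator of the death tables but remain in the FAS. Protocol 11.6.3 promises a death rate covering any death, and the synopsis places that rate under the primary objective. Tables restricted to patients who yielded a safety record may not deliver it, and one report could show two death counts with no explanation.

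**Working it through.** The plan states no death rate, no event target and no number excluded, so there is no figure to reproduce. The check is of direction and plausible size.

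**Direction.** Let N be treated patients, D deaths among them, k treated patients outside the Safety Set, and j of those k who died.

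- FAS death rate: D/N. Safety Set death rate: (D − j)/(N − k).
- The tabulated count falls by j, so it can only be equal or lower.
- (D − j)/(N − k) < D/N exactly when j/k > D/N. The rate falls if the excluded patients died more often than treated patients overall. If all of them died (j = k), it always falls.
- An excluded patient has no recorded adverse event, so dropping k patients multiplies every adverse-event incidence by N/(N − k).

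**Inputs.**

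- N = 2238 enrolled (protocol 4.1). The number treated is not given; I take all as treated.
- Death proportion 8.4% at a median of 51 weeks, from the INC424 arm of COMFORT-I (protocol 1.3.5), borrowed for illustration. D = 0.084 × 2238 = 188.
- k = 2 or 6 (0.1% or 0.25% of 2238, rounded): assumptions.
- Ceiling for deaths before the Week 4 visit, assuming a constant hazard: 188 × 4/51 = 14.7, about 15 deaths from all causes.

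| k | All k died: (188 − k)/(2238 − k) | None died: 188/(2238 − k) | AE incidence × 2238/(2238 − k) |
|---|---|---|---|
| 0 | 188/2238 = 8.40% | 8.40% | 1.000 |
| 2 | 186/2236 = 8.32% | 8.41% | 1.001 |
| 6 | 182/2232 = 8.15% | 8.42% | 1.003 |
| 15 (ceiling) | 173/2223 = 7.78% | 8.46% | 1.007 |

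The last row requires that no patient dying in the first four weeks has any post-dose safety record. It is a bound, not an expectation.

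**How a patient can fall out.** All of these must hold: no Day 1 post-dose adverse-event entry, not even a nil one; no later adverse-event, SAE or laboratory record; and a reading under which a Death form is not safety data.

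**The case against.** The strongest reply is that a patient handled according to protocol enters the Safety Set on Day 1. Protocol 7.5.1.1 has the first dose given at that visit, with monitoring for adverse events and recording in the eCRF. Table 7-1 marks adverse events for database entry at Day 1, and SAP 2.3 treats every assessment after baseline as post-baseline. Protocol 7.6 also requires safety contact during the 28 days after the last dose, and a fatal SAE is itself safety data. This stands: it makes the route narrow. It does not close it, because the rule still acts whenever those records are missing.

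Two stronger readings are tempting.

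- A reader might infer that early deaths vanish from the safety results. They do not: SAP 3.4.1.2 and 3.5.1 list all deaths. The gap is in the tabulated summaries.
- A reader might infer that a sizeable share of deaths is lost. The documents give no basis for this. On the borrowed rate about 15 deaths of any cause fall in the first four weeks. Losing 11 (0.5% of 2238) would need 11/15 = 73% of them to lack any safety record, and losing 22 (1%) exceeds the total.

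Nor does the note on differing counts prove that the analysis sets are the only cause. It refers to efficacy analyses in general. In PFS a death after progression is not the event, and duration of response counts only death due to myelofibrosis (SAP 3.4.3), so counts can differ even with identical sets. OS inclusion is itself conditional: SAP 3.4.3 takes deaths up to the study completion evaluation visit, and the date rules do not say what applies when that visit never occurs.

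Finally, the study is descriptive with no hypothesis test, so no formal conclusion turns on the choice.

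**Conclusion.** The point holds in a limited form. The Safety Set selects on a post-treatment outcome, the death tables and the primary adverse-event denominator use it, and OS does not. A treated patient who dies with only a Death form can be missing from the death tables while listed and possibly counted in OS. The documents leave the status of the Death form open.

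The size cannot be determined from the documents; it is probably small and may be zero. The illustration gives a fall of 0.1 to 0.25 percentage points for 2 to 6 excluded deaths. It assumes that all enrolled patients were treated, that the COMFORT-I death proportion applies, and that every excluded patient died. The effect on adverse-event incidence over that range is a relative rise of 0.1% to 0.3%. This is a free improvement to an analysis-set definition, not a threat to the trial's conclusions.

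**What to change.** Preferred: in SAP 2.1, define the Safety Set as all patients who received at least one dose, making it equal to the FAS, and record the departure from protocol 11.2 in SAP section 4, which already records the changed transfusion definitions.

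Minimum: keep the set, tabulate deaths on all treated patients, and state that death counts as post-baseline safety data.

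In either case:

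- report the number of treated patients with no post-baseline safety record, and how many of them died;
- replace the note in SAP 3.4.1.2 with a short reconciliation of the safety and OS death counts, naming any difference due to the analysis set, the death-date windows or a missing completion visit.

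The cost is one definition or sentence in the SAP and one small table. No new data are needed, and incidence figures may shift very slightly. If the sponsor prefers to change protocol 11.2 itself, that needs an approved written amendment under protocol 12.11; the minimum version avoids this.
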